3.5 Justification of choice of study population

This study will only observe surgical procedures that would have been done in the same manner independently from the present study. The study neither interferes with the treatment nor with the usual clinical follow-up procedures. Therefore, the study population is also not determined based on certain criteria other than their willingness to allow cost data to be collected.

4 PROJECT OBJECTIVES AND DESIGN

4.1 Overall objective

This prospective study intends to examine quality of life, costs and the cost-utility ratio from the health care system and societal perspectives at the Schulthess Klinik one year after surgery of the CMC I using the Touch® implant.

4.2 Primary Objective

The primary objective is to evaluate if the CMC I arthroplasty using the Touch® implant is cost-effective compared to the RSI arthroplasty in terms of an acceptable incremental cost-effectiveness ratio (ICER). To calculate the ICER, the following data are required:

- Costs:
 - o Direct medical costs taken from the clinic's billing system

Clinical Study Protocol CUA Touch [name], v

[name], v4.0 from 12.02.2021

- Indirect costs associated with loss of productivity measured with the Work Productivity and Activity Impairment Questionnaire (WPAI) [5]
- Utilities:
 - o QALYs will be derived from the EuroQol EQ-5D five level (EQ-5D-5L) questionnaire [6].

4.3 Secondary Objective

As a secondary objective we want to determine whether direct medical costs are higher with the Touch® implant compared to RSI arthroplasty. Cost-effectiveness regarding pain ADL will be evaluated as the difference in costs over the difference in pain ADL between both interventions. We will analyse return to work after surgery in both groups. Lastly, we will compare the clinical and patient-reported outcomes after surgery for both groups.

4.4 Safety Objectives

The study aims to assess the safety of the Touch® implant. At each follow-up for a total span of a year, the investigator will assess whether any AEs have occurred and document them electronically in the Adverse Event / complication form [29], whether or not the investigator concludes the event to be related to the treatment.

5 STUDY OUTCOMES

5.1 Primary Outcome

The primary research outcome is the cost-utility of the Touch® compared to the RSI arthroplasty in terms of an acceptable incremental cost-effectiveness ratio (ICER).

To calculate the ICER, the following data are required which will be collected at all timepoints but the surgery:

- Costs:
 - o Direct medical costs taken from the clinic's billing system
 - Indirect costs associated with loss of productivity measured with the Work Productivity and Activity Impairment Questionnaire (WPAI) [5]
- Utilities:
 - Utilities (QALYs) will be derived from the EuroQol EQ-5D five level (EQ-5D-5L) questionnaire [6]

Costs

Direct medical costs (inpatient and outpatient) accruing at Schulthess Klinik will be gained from the Schulthess Klinik hospital accounting system (Kostenträgerrechnung).

In the hospital cost accounting system, costs per patient are calculated according to Swiss cantonal standard procedures [26]. The accounting system contains the costs for labour (physicians, nurses, therapists) and materials (implants, instruments, etc.). We will also inquire whether any costs accrued externally, e.g. through therapy sessions by asking for the number of external therapy sessions. These

costs will be taken into account by multiplying the amount of sessions with mean therapy costs. Some additional cost elements (e.g. for administration) are allocated as a fixed rate to each patient. In the previously conducted study (KEK-ZH Nr. 2013-0381) [10] [submitted], medical cost data were collected from Swiss health insurances. These cost data cannot be used for our comparison since they also contain costs of other health-related conditions such as comorbidities. Therefore, we will report the medical costs of patients who will undergo a RSI arthroplasty over the duration of our study. This will give us a precise assessment of how much a RSI arthroplasty costs today and allow for better comparisons between the two procedures. An overview of the three cohorts can be seen in Figure 2.

Figure 2: Overview of the medical cost data composition in our study.

Information on productivity losses will be gained using the Work Productivity and Activity Impairment Questionnaire – Specific Health Problem V 2.0 (WPAI-SHP) [5] and additional questions on work status and personal income.

The WPAI-SHP consists of 6 questions which allow to calculate the productivity losses caused by the specific health problem in the last seven days because of absenteeism (absence from work) and presenteeism (reduced productivity when at work). Consequences of the specific health problem on the ability to carry out regular daily activities, other than work, are also assessed. The WPAI-SHP was tested for validity and reliability for various disorders and can be easily adapted to a specific health problem by replacing the word "problem" by the name of the problem. In this study, we will also use the German and English version and insert the word "Daumenbeschwerden" or "thumb problems" at the appropriate places.

In addition to the WPAI-SHP, patients will be asked to report their current work status and income. Questions on current work status include 1) the number of hours usually worked in a week, 2) whether level of employment was reduced due to the health problem, 3) the duration of the absence from work after surgery and 4) current monthly personal income in brackets of 2'000 Swiss Francs (CHF) up to 16'000 CHF. The questions on personal income has been adapted from a previous population based survey on low back pain [27] and is similar to the question used in the Swiss Health Survey. The monetary value of productivity losses will be calculated by combining the WPAI-SHP with the questions on work status and income (www.reillyassociates.net).

Pricing, perspective and discounting

We will present direct and indirect medical costs in Swiss Francs. We will choose the hospital and the social perspective. Thus, our results can primarily inform decision makers within the hospital and local authorities about the costs of service provision and health related costs for society. Costs will not be discounted due to the short time frame. Current standards for performing health economic evaluations are applied [28].

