	- Patients with concomitant surgery at another joint at the hand in the same session				

Measurements and procedures:	 We will compare the cost-utility of the Touch® implant to the RSI arthroplasty in terms of an acceptable incremental cost-effectiveness ratio (ICER). Follow-up timepoints: At baseline (Inclusion) and 6 weeks, 3 months, 6 months, and 1 year after surgery. 				
Study Product / Intervention:	 Analysis of questionnaires and medical costs to evaluate the cost-utility of the Touch® implant in patients compared to a RSI arthroplasty. Questionnaires will be sent to the patients at baseline and 6 weeks, 3 months, 6 months and 1 year after surgery. The patients will undergo clinical examinations at the same timepoints except for the 6-month follow-up appointment at which they will only fill out the questionnaires. As comparison group, we will use outcome data of a previous cohort of patients who had a RSI arthroplasty and were working (n=42), (KEK-ZH Nr. 2013-0381) [10] [submitted]. This outcome data is already available and will not have to be collected. The cost data will be derived from patients undergoing a RSI arthroplasty during the timeframe of this study and retrospectively matched and assigned to the control group. 				
Control Intervention (if applicable):					
Number of Participants with Rationale:	There will be a total of 80 patients receiving a Touch implant included in this study. Rationale: See Statistical Considerations				
Study Duration:	The data collection period from first patient first visit (FPFV) to last patient last visit (LPLV) will be 3.5 years. Including study preparation and writing of the final report, the study will last 5 years.				
Study Schedule:	03/21 First-Participant-In (planned) 09/24 Last-Participant-Out (planned)				
Investigator(s);	Dr. med. [name], MHA Schulthess Klinik [name] [name] E-Mail: [contact]				
Study Centre(s):	Single-center study. Clinic: Schulthess Klinik [name]				

Statistical	For sample size estimation, we used the EQ-5D-5L score, which is required			
	to calculate the ICER. A 2-sided two-sample means test (Satterthwaite's t			
constactations,	test assuming unequal variances) was applied. Alpha was set at 0.05 and the power at 0.90.			

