7.3 Assignment to study groups

All patients who fulfil the inclusion criteria will be considered for the study. Since this study utilises data of a previous study for the comparison group all the recruited participants will be assigned to the intervention group.

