9 STUDY ASSESSMENTS

9.1 Table of study procedures and assessments

				Follow-up time	points and range	S
	Screening/Baseline (Study start)	Surgery	6 weeks 42 days (±7)	3 months 91 days (± 14)	6 months 182 days (± 21) ¹	1 year 365 days (± 30)
Patient groups	Touch® group	Touch® group	Touch® group	Touch® group	Touch® group	Touch® group
Patient Information / Informed Consent	X					
Demographics	Х					
Diagnosis / Pre-treatment	X					
Surgery / hospital stay		х				
Radiology	X	x	х	x	2	х
Clinical examination Range of motion Kapandji index Grip Strength Key pinch test	x		x	×		x
Patient questionnaires Work status / salary ¹ WPAI ¹ Functional outcomes EuroQoL EQ-5D-5L Satisfaction (after surgery) Pain score Physical work demands	×		x	×	x	x
Complications / AEs		х	х	x	х	x
Direct medical costs		x	x	x	x	x

¹ The work status/salary and WPAI questionnaires as well as the direct medical costs are evaluated solely because of this study. The same goes for all the items (patient questionnaires, complications/AE, direct medical costs) listed under the 6-month follow-up timepoint. Everything else is standard procedure at the clinic.

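### The protocol does not secure direct costs on the same basis in both arms: it gives no route for obtaining external therapy costs from the RSI cost patients, and it sets them no eligibility rule or 365-day cost window

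*Protocol*

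**What the plan says.** **Cost components.** Section 5.1 starts from costs "accruing at Schulthess Klinik will be gained from the Schulthess Klinik hospital accounting system". It then adds external therapy by asking for session numbers ("We will also inquire whether any costs accrued externally, e.g. through therapy sessions by asking for the number of external therapy sessions"), and says these "costs will be taken into account by multiplying the amount of sessions with mean therapy costs". It does not say which patients are asked.

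**Source of RSI costs.** The insurer costs of the earlier RSI cohort are set aside because they include other conditions. Section 5.1 continues: "Therefore, we will report the medical costs of patients who will undergo a RSI arthroplasty over the duration of our study". The Synopsis (Study Product / Intervention) describes these as patients "undergoing a RSI arthroplasty during the timeframe of this study and retrospectively matched and assigned to the control group". Section 8.1.2, by contrast, reads as if cost data are still to be gathered for the historical group itself.

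**Who is contacted.** Section 7.3 states that "all the recruited participants will be assigned to the intervention group". Every column of the section 9.1 schedule is headed for the Touch group. Section 11.1.2 names one source for costs, the TIP HCe system, and no patient form.

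**Timing.** Section 5.1 introduces the ICER data as items "which will be collected at all timepoints but the surgery". In section 9.1 the row "Direct medical costs" is marked at surgery and at each follow-up, but not at baseline.

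**The concern.** The cost difference is the numerator of the primary ICER (section 10.4.2). The direct part of it is also the subject of a secondary objective (section 4.3). If one arm's cost contains a component that the other arm's cost lacks, the difference is biased whatever the sample size. Sessions that nobody asked about during follow-up cannot be recovered at the analysis stage.

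The RSI cost patients are also loosely defined. Section 7.1 sets criteria for Touch recruits and describes the comparison group as patients of the earlier study. It sets none for the concurrent RSI patients who supply the costs, and no section states how long their costs are followed.

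**Working it through.** **1. The plan's own figures.** The protocol states no cost figure. The relevant input is the 1-year utility gap in section 10.2: 0.96 − 0.91 = 0.05. The sample size built on it reproduces. With 42 controls, SDs 0.09 and 0.05, two-sided alpha 0.05 and a Satterthwaite t test, 68 Touch patients give power 0.9003 and 67 give 0.8997; 68 / 0.85 = 80. Nothing here disputes those numbers.

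**2. The arms side by side.**
- Clinic-accrued costs: same accounting system for Touch and for RSI.
- External therapy: Touch patients have questionnaires and visits at which they can be asked. For the RSI cost patients no consent, questionnaire or visit is described.
- Eligibility: section 7.1 applies to Touch. None is stated for the RSI cost patients.
- Cost window: Touch is scheduled to 365 days. None is stated for RSI.

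**3. Error from the missing component.** Let C be mean clinic cost, E mean external cost, T Touch and R RSI.
- Intended difference: (C_T + E_T) − (C_R + E_R).
- Difference if only Touch is asked: (C_T + E_T) − C_R.
- Error: + E_R, the RSI external cost left out. It does not depend on E_T.
- Shift in the ICER: E_R / ΔQALY. Productivity costs add to the numerator separately and do not change this shift.

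**4. Size per CHF 100.** The protocol gives no planned QALY difference, so two values are assumed.
- The 0.05 gap holds all year: ΔQALY = 0.05 × 1 = 0.05, and 100 / 0.05 = CHF 2,000 per QALY.
- The gap grows linearly from zero: ΔQALY = 0.05 × 1/2 = 0.025, and 100 / 0.025 = CHF 4,000 per QALY.

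**5. Illustration only.** Neither session counts nor prices are in the protocol. Assume 5 to 15 sessions at CHF 50 to 150.
- Cost left out: 5 × 50 = CHF 250 to 15 × 150 = CHF 2,250.
- Shift at 0.05: CHF 5,000 to 45,000 per QALY.
- Shift at 0.025: CHF 10,000 to 90,000 per QALY.

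For orientation, section 3.1 cites thresholds of USD 50,000 to 150,000.

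**6. Cost window.** The planned last-participant-out date is 09/24. An RSI operation after about 09/23 has under a year of costs at that date. If such patients are used with incomplete costs, C_R is too low and the error has the same direction as in step 3.

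**The case against.** Several counter-arguments have force.

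- **Who is asked is not stated.** A reader might infer that the protocol restricts the external-therapy question to Touch. It does not say so. Section 8.1.2 leaves cost data to be collected for the control side, and Figure 2, on the composition of the cost data, is not available here. That external therapy would be counted for Touch only is therefore an inference, though no contact with the RSI cost patients is described anywhere.
- **Intervals on matched pairs.** A reader might infer that assigning one patient's cost to another's QALY invalidates the analysis. The protocol specifies no interval, and its point ICER depends only on arm means, so the pairing does not alter it. Matching variables may properly sit in a statistical analysis plan.
- **Implant and stay.** A reader might infer that section 5.1 drops the index operation from the costs. The same section counts inpatient costs and implants, and section 9.1 marks direct costs at surgery. The sentence suits the questionnaires and is a wording slip for the costs.
- **Eligibility and window.** Matching to working controls may carry some criteria over. Section 4.1 sets a one-year horizon, and the funding agreement is expected to run to October 2025 (section 13.1), so a later cost extract is possible. None of this is written as a rule for the RSI cost patients.
- **Relative size and direction.** Productivity may dominate. The cited absences differ by 54 − 20 = 34 days, or 34 × 12/365 = 1.118 months. At assumed monthly incomes of CHF 2,000 to 16,000, taking these as calendar days, that is about CHF 2,200 to 17,900. The bias also runs against Touch and so is conservative for the alternative hypothesis. But it favours a finding of higher direct costs with Touch under section 4.3, and a cost-utility ratio is meant to be estimated without bias in either direction.
- **Planned sensitivity analyses.** Section 10.4.2 varies assumptions on direct costs. That does not repair a base case whose components differ by arm.

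Using a separate RSI cost cohort is itself disclosed and reasoned, and is not the fault.

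**Conclusion.** The point holds as a gap in how comparable costs are secured. No described route yields external therapy sessions for the RSI cost patients, so as written the component would probably enter for Touch only and overstate the Touch-minus-RSI difference. The size is unknown: CHF 2,000 or 4,000 per QALY for each CHF 100 left out per RSI patient, under assumed QALY differences of 0.05 or 0.025 in favour of Touch. The wider ranges in the working rest on assumed session counts and prices, so they are not an estimate of the bias.

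The missing eligibility rule and 365-day window for the RSI cost patients are part of the same gap. The effect of the window would run in the same direction; the effect of eligibility could run either way. The surgery wording in section 5.1 and the conflict between section 8.1.2 and the Synopsis and section 5.1 need correction, but are matters of consistency.

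**What to change.** 1. **Same components, same window.** Count direct costs in both arms from the index operation, with stay and implant, to day 365. Either (a) put the external-therapy question to the RSI cost patients in the same way as to Touch patients, or (b) use clinic-accrued costs only in the base case and move external therapy to a sensitivity analysis. Option (a) needs consent and contact with the RSI patients, and must start while they are in follow-up. Option (b) needs only wording, but gives a base case narrower than the social perspective chosen in section 5.1.
2. **Define the RSI cost cohort.** Apply the relevant section 7.1 criteria (working, primary osteoarthritis, no revision, no additional surgery beyond the exception allowed there) and use only operations with 365 days of cost data. This is a filter on the accounting extract plus a check of working status. The RSI cost sample may be smaller.
3. **Reconcile the text.** Align the timing sentence in section 5.1 with section 9.1 for direct costs. Make section 8.1.2 agree with the Synopsis and section 5.1 on whose costs are collected.
4. **Only if an interval is reported:** do not treat assigned RSI costs and historical QALYs as pairs observed within the same patient.

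### The protocol gives no route to external therapy costs for the RSI cost cohort, so as written this item risks entering the Touch cost total only

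*Protocol*

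**What the plan says.** Protocol section 5.1 builds direct medical cost from two sources. The first is the clinic's patient-level accounting system, which covers what is spent at the clinic. The second is care received elsewhere: "We will also inquire whether any costs accrued externally, e.g. through therapy sessions by asking for the number of external therapy sessions". It is valued simply: "costs will be taken into account by multiplying the amount of sessions with mean therapy costs". No group is named for this question.

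The comparison costs come from a third cohort. Section 5.1 rules out the insurer data of the previous RSI study because they include costs of other conditions, and continues: "Therefore, we will report the medical costs of patients who will undergo a RSI arthroplasty over the duration of our study". The study synopsis describes these as "patients undergoing a RSI arthroplasty during the timeframe of this study and retrospectively matched and assigned to the control group". Section 8.1.2 says that cost data are all that remains to be collected for the control group, without saying what those data contain.

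On contact with patients, section 7.3 states that "all the recruited participants will be assigned to the intervention group". The study schedule and the table in section 9.1 carry Touch columns only. Section 2.6 requires consent before any study procedure. No consent, visit or questionnaire is described for the RSI cost cohort. The source table in section 11.1.2 lists one source for costs, the costing system TIP HCe.

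On perspective, section 5.1 says "We will choose the hospital and the social perspective", while section 4.1 speaks of the health care system and society.

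**The concern.** A cost difference is interpretable only if both totals contain the same items. External therapy can be counted only by reaching the patient or searching a record that holds it. For Touch patients there is a questionnaire channel at every follow-up. For the RSI cost cohort there is none, and the one earlier source that might have held outside therapy has been set aside.

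If the item is counted on one side only, three results are affected: the numerator of the primary cost-utility ratio (section 10.4.2), the numerator of the cost-per-pain-point ratio (section 10.4.3), and the secondary objective in section 4.3, which asks whether direct medical costs are higher with Touch. In the last of these the artefact pushes towards a yes. Once follow-up of the RSI cohort is over without the count, wording in an analysis plan cannot supply it.

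**Working it through.** **Passages side by side**

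| | Touch | RSI cost cohort |
|---|---|---|
| Costs at the clinic | Accounting system (5.1) | Accounting system, as the general source for direct costs (5.1) |
| External sessions | By asking (5.1); questionnaires at each follow-up (9.1) | No consent, contact or record search described |
| Link to the study | Recruited (7.3) | Matched and assigned afterwards (synopsis) |

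**What the error is.** Let E_T and E_R be the mean external therapy cost per patient under Touch and RSI.

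- Correct contribution to (Cost Touch − Cost RSI): E_T − E_R.
- Contribution if only Touch is counted: E_T.
- Error: E_T − (E_T − E_R) = **E_R**, always zero or positive.

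So the error is the omitted RSI cost. It raises the Touch-minus-RSI difference and vanishes only if RSI patients use no external therapy.

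**Inputs.** The protocol gives neither session counts nor a price, so it has no figure of its own for this item to reproduce. Assumed: 2 to 10 RSI sessions per patient at CHF 50 to 150 each. For the denominator, section 10.2 gives planning values of 0.96 and 0.91, a difference of 0.05. Held for a full year this is 0.05 QALY. A smaller gain of 0.02 QALY is assumed for comparison.

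The sample size built on that 0.05 does reproduce. With 42 controls and SDs of 0.09 and 0.05, the Satterthwaite t test has power 0.8997 at 67 Touch patients and 0.9003 at 68, and 68 / 0.85 = 80. It rests on EQ-5D-5L alone and is not touched by this point.

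**Shift in the ICER** = E_R / QALY difference:

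| RSI sessions × price | E_R (CHF) | at 0.05 QALY | at 0.02 QALY |
|---|---|---|---|
| 2 × 50 | 100 | 2,000 | 5,000 |
| 5 × 100 | 500 | 10,000 | 25,000 |
| 10 × 150 | 1,500 | 30,000 | 75,000 |

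Section 3.1 quotes thresholds of USD 50,000 to 150,000. No conversion from CHF is made here, so this compares order of magnitude only.

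**Effect of a clinic-only base case.** Leaving the item out of both arms gives a contribution of 0, so the error is 0 − (E_T − E_R) = E_R − E_T. This is nil when external use is equal, and smaller in size than E_R whenever 0 < E_T < 2 × E_R. If Touch patients used more than twice the external therapy of RSI patients, the clinic-only difference would be further off than the one-sided count.

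**The case against.** A reader might infer that the protocol restricts the question to Touch patients and that RSI costs are simply read back from the clinic's accounts. The text does not say either. Section 5.1 describes one costing method without naming a group. Section 8.1.2 leaves room for further cost collection on the control side. In the synopsis, the word for looking back describes the matching and assignment, not the capture of costs. Figure 2, which shows how the medical cost data are composed, is not available in the text at hand and might settle it.

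The argument from silence also has limits. The source table and the questionnaire contents in sections 9.2.2 and 9.2.4 do not list an external therapy item for Touch patients either. Those lists alone would suggest that nobody is asked. What supports an imbalance is narrower: section 5.1 says the question will be put, and the only patients with a described channel for it are Touch patients.

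A reader might also take the whole Touch external cost as the distortion. That is wrong: Touch patients' external therapy is a real cost of Touch, and only the missing RSI counterpart is an error.

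Two further defences are weaker. Section 10.4.2 plans sensitivity analyses on direct medical costs, and varying RSI sessions would fit there, but that line does not name the item or correct the base case. And a bias against Touch is conservative for the hypothesis in section 10.1, but not for the objective in section 4.3.

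External therapy is not out of place in every perspective: it belongs in a societal or health care system result, in both arms. Nothing says it enters a hospital-only result.

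**Conclusion.** The gap is real: the protocol plans to count external therapy by asking patients and describes no way of doing so for the cohort that supplies the RSI costs. That the item will be counted in Touch alone is what follows if the plan is carried out as written. It is not a stated rule.

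If that happens, the cost difference is too high by the mean RSI external cost. Under the assumed ranges this is CHF 100 to 1,500 per patient, or CHF 2,000 to 30,000 per QALY at 0.05 QALY and CHF 5,000 to 75,000 at 0.02 QALY. The effect may be negligible or may matter for the conclusion; the documents do not allow a narrower statement. Besides the counts and prices, this rests on the assumed QALY gain being positive and on the one-year utility difference standing in for a full-year QALY difference.

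**What to change.** State in section 5.1 that the base-case direct cost contains only items captured the same way in the Touch cohort and the RSI cost cohort, and say which items these are.

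Include external therapy in the societal or health care system result only if RSI counts are obtained equivalently: the same session question to both cohorts, or therapy prescriptions in the clinic record for both. Otherwise report the Touch figure separately and add a sensitivity analysis that varies RSI sessions relative to the Touch mean, for example at 0.5, 1 and 2 times.

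The cost is protocol wording, plus one question or a record search for the RSI cohort if the item is to be kept. Putting the question to RSI patients would also need a described contact and consent route. The decision should be made while those patients can still be reached.

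The downside is that, without RSI counts, the base case omits external therapy in both arms. If the share of therapy done outside the clinic differs by arm, the clinic-only difference is incomplete, and the sensitivity analysis should show by how much.
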